6.6.2 Prohibited Medications

The following medications are prohibited throughout the duration of the study:

- azathioprine, 6-mercaptopurine, methotrexate and thalidomide;
- cyclosporine, mycophenolate and tacrolimus;
- interferon and
- anti-TNF α therapy/other biological treatment;
- intravenous corticosteroids or rectally administered formulation of corticosteroids or 5-ASA.
- Oral JAK inhibitors (except the trial medication)

In addition, concomitant administration of CYP3A inducers and moderate to potent CYP3A inhibitors with systemic effects should be avoided for the duration of the study.

Examples of medications that are prohibited from use from 28 days prior to the first dose of study medication until completion of follow up period, due to potential for drug interactions or confounding of data interpretation, are listed in [Appendix 4](#).

All live vaccines immunization are prohibited from signing of informed consent, throughout the duration of the study, and for 1 month after last dose of study medication.

6.6.3 Traditional Chinese and Herbal Medicines

The following categories of traditional or herbal medicines are prohibited at Visit 1 and any time during the study:

- Traditional or herbal medicines used for the treatment of UC, including those that investigator believe to contain corticosteroids.
- Traditional or herbal medicines that have known effects on platelets and that increase the tendency to cause bleeding.

6.7 Treatment after study completion

The investigator is responsible for ensuring that consideration has been given to the post-study care of the patient's medical condition whether or not Reistone Biopharma/designated CRO is providing specific post study treatment after week 16. Reistone Biopharma/designated CRO has provided an 8-week extension phase of active therapy, and will not provide post-study treatment after the extension phase. Post-treatment UC therapy should not be entered into the eCRF.

6.8 Study Drug Overdose Management

An overdose is defined as a dose greater than the total doses described above which results in clinical signs and symptoms. These should be recorded by the investigator on the AE/SAE pages. In the event of an overdose of study medication, the investigator should use clinical judgment in treating the overdose and contact the study medical monitor.

Reistone Biopharma/designated CRO is not recommending specific treatment guidelines for overdose and toxicity management. The investigator is advised to refer to the relevant document(s) for detailed information regarding warnings, precautions, contraindications, adverse events, and other significant data pertaining to the study drug being used in this study. Such documents may include, but not be limited to, the IB or equivalent document provided by Reistone Biopharma/designated CRO.

7. Study Assessments and Procedures

7.1 Critical Baseline Assessments

The following critical baseline assessments will be conducted at Visit 1:

- Demographic history (including gender, ethnic origin, date of birth, height and weight)
- Medical history of Ulcerative Colitis comprised of date of diagnosis (year of diagnosis is acceptable) and previous and/or current medical conditions
- Physical examination
- Heart rate, blood pressure, and body temperature measurement
- 12-Lead ECG
- Chest x-ray (or historical chest x-ray/CT-Scan obtained within 3 months of Screening (Visit 1))
- Clinical laboratory assessments (including chemistry, hematology, pregnancy test)
- Mayo Score – Mayo Scoring System for Ulcerative Colitis. 9-point modified Mayo score will be used to confirm patient eligibility for the study at baseline. The duration of the time between endoscopy and baseline should not exceed 10 days. Mayo score and Partial Mayo score will also be calculated and collected prior to randomization.

7.2 Efficacy Endpoints Assessments

7.2.1 Primary Efficacy Endpoints

The percentage of subject achieve clinical response at week 8, defined as decrease from baseline in 9-point modified Mayo score of at least 2 points and at least 30%, with an accompanying decrease in the subscore for rectal bleeding of at least 1 point or absolute subscore for rectal bleeding of 0 or 1.

7.2.2 Secondary Efficacy Endpoints

- The percentage of subjects achieve clinical remission per 9-point modified Mayo score at week 8, where stool frequency subscore ≤ 1 , rectal bleeding subscore of 0, and endoscopic subscore ≤ 1

- The percentage of subjects achieve clinical remission at week 8 as per total Mayo score of 2 points or lower than 2, with no individual subscore exceeding 1 point and a rectal bleeding subscore of 0.
- The percentage of subjects achieve endoscopic remission (mucosal healing) at week 8, defined by Mayo endoscopic subscore \leq 1 point.
- Change from baseline in 9-point modified Mayo score at week 8.
- Change from baseline in total Mayo score at week 8.
- Change from baseline in partial Mayo score (Mayo score without endoscopy) at week 1, 4, 8, 9, 12 and 16.
- Change from baseline in the level of biomarkers CRP, fecal calprotectin.
- The systemic exposure of SHR0302 in steady state in Ulcerative Colitis patients (i.e. concentration and area under the curve).

7.2.3 Safety Endpoints

- To evaluate the safety and tolerability by laboratory parameters.
- To evaluate the safety and tolerability by collection of AE/SAE incidence
- To measure the vital signs (BP, HR, and Body temperature)
- To measure subject's total lipid profile, which includes Triglyceride, LDL and HDL.
- To measure subject's thyroid profile: TSH, free T4 and free T3.
- 12 -lead ECG.

7.2.4 Patient Diary Assessment

Subjects will be provided with an electronic diary at screening visit in order to collect the patient reported outcome components of the total Mayo score (see [Appendix 1](#)), including the following information:

- 'Normal' number of stools per day, when not having a flare, and will be collected only once.
- Number of stools currently per day.
- Presence of rectal bleeding currently (if any).

Diary data will be assessed at the clinic, at each study visit from baseline (Day 0) until the end of follow up period (Week 18). The information extracted will be used for calculation of Mayo score taking into account the data recorded over the last 3 days prior to each study visit. Should any bowel preparation be required to perform the endoscopy examination (colonoscopy), last 3 days patient diary must be completed and assessed prior to any bowel

preparations. If data on any of these days is missing, the last 3 days closer to that day of bowel preparation/visit within the last 7 days before the day for bowel preparation/visit will be used for calculation. In order to encourage consistent diary recording, subjects are required to enter diary data continuously throughout the study.

7.2.5 Mayo Score Assessment

Mayo score is an instrument designed to measure disease activity of ulcerative colitis. Mayo score ranges from 0 to 12 points. It consists of 4 subscores, each graded from 0 to 3 with higher scores indicating more severe disease (see [Appendix 1](#))

- stool frequency (0-3)
- rectal bleeding (0-3)
- findings of colonoscopy (0-3)
- physician global assessment (PGA) (0-3)

Mayo score is assessed at baseline and Week 8. If the subject scores ≥ 2 on the endoscopic sub-score of the Mayo Score at baseline and meet all other inclusion/exclusion criteria, the subject will be randomized. Should any bowel preparation be required to perform the colonoscopy, 3-day patient diary must be completed and assessed prior to any bowel preparation. For the baseline endoscopy, the duration of the time between endoscopy and baseline should not exceed 10 days. Baseline (Day 0 -Visit 2) endoscopy images/films (eligibility assessment) and Week 8 endoscopy images/films will be submitted to central lab for central reading. The central lab will send eligibility report to confirm eligibility.

The physician global assessment (PGA) acknowledges the three other criteria: the patient's daily recollection of abdominal discomfort and general sense of wellbeing, and other observations, such as physical findings and the patient's performance status.

Clinical response is defined as a decrease from baseline in Mayo score of at least 3 points and at least 30 percent, with an accompanying decrease in the subscore for rectal bleeding of at least 1 point or absolute subscore for rectal bleeding of 0 or 1. Clinical remission is defined as a total Mayo score of 2 points or lower, with no individual subscore exceeding 1 point.

Endoscopic response is defined as decrease from baseline in the findings of the colonoscopy subscore of the Mayo Score ≥ 1 . Endoscopic remission is defined as the findings of colonoscopy subscore of the Mayo score equals 0.

7.2.6 9-point Modified Mayo Score

9-point modified Mayo score is the Mayo score excluding physician global assessment (PGA) subscore, hence the maximum is 9 points and minimum 0 point. By removing the PGA, it removes the subjective view/assessment from the physicians hence reducing bias. It is also a recommended assessment by the regulators. 9-point modified Mayo score will be collected as a primary endpoint at baseline (Visit 2) and week 8 (Visit 5). This has been advised by the US FDA according to FDA guidance on ulcerative colitis trial ([10](#)).

7.2.7 Partial Mayo Score Assessments

A partial Mayo score (Mayo score without endoscopy component) will be assessed at baseline, week 1, week 4, week 8, week 9, week 12, week 16 and week 18, as secondary endpoints.

7.2.8 Colonoscopy

Endoscopy examination (colonoscopy) will be required at baseline and Week 8 and it will be performed in order to establish Mayo endoscopic subscore and confirm patient eligibility for the study at baseline. The duration of the time between endoscopy and baseline should not exceed 10 days. As per Surveillance Guidelines for patients with ulcerative colitis, all subjects who have not had colonoscopy performed within last 10 years from onset of symptoms will require colonoscopy procedure for screening surveillance. An appropriately trained endoscopist should perform the colonoscopy. Where possible the same endoscopist should perform the endoscopy for both baseline and Week 8 visits, where this is not possible it should be clearly documented who performed each endoscopy procedure.

7.3 Safety Assessment

7.3.1 Vital Signs

Vital signs measurements will include heart rate and systolic and diastolic blood pressure, and body temperature. Vital signs will be obtained after subjects have rested for approximately 5 minutes and before performing ECG. A single set of values will be obtained.

Vital signs will be performed using equipment provided by investigational sites and will be obtained at visits and time points as detailed in the [Section 5.12 –Time and Event Table](#).

7.3.2 12 lead ECG

12-lead ECG measurement and rhythm strip (10 seconds) will be obtained after measurement of vital signs. Triplicate ECG measurements are collected at rate of 3 ECGs over 5 minutes period. After vital signs are obtained subjects should be placed in the supine position for the ECG measurements.

ECG measurements will be taken at various visits and time points as detailed in [Section 5.12 –Time and Event Table](#). The investigator, a designated sub-investigator, or other appropriately trained site personnel will be responsible for performing 12-lead ECG assessments. The investigator must provide his/her dated signature on the original paper tracing, attesting to the authenticity of the ECG machine interpretation. The investigator will review the ECG and determine if the subject should continue the study.

7.3.3 Tuberculin Test (PPD)

Subjects must have a screening tuberculin test (PPD) administered and then evaluated by a health care professional (nurse or doctor) 48 to 72 hours later in order to be eligible for the study, unless performed and documented within the last 3 months. The test consists of intracutaneous injection of Tuberculin, concentration as per local medical standard of practice, on the volar aspect of the forearm, using a short beveled 26- or 27- gauge needle (Mantoux test). The test is positive if the induration's diameter (not erythema) is ≥ 5 mm 48 to 72 hours after injection. Subjects who have previously received BCG vaccination will be tested by QuantiFERON Gold/or T-Spot test in place of Mantoux PPD and have these results determine patient eligibility for participation.

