5.2 Inclusion Criteria

Subjects must meet all of the following inclusion criteria to be eligible for enrolment into the study;

1. Male and Female subject age ≥ 18 and ≤ 75 years of age at randomization.
2. Active ulcerative colitis with a 9-point modified Mayo score of 5 to 9 points and endoscopic subscore of 2 to 3 (The duration of the time between endoscopy and baseline should not exceed 10 days and allow central over read turn over before randomization).
3. Subject should have at least three-month history of Ulcerative Colitis diagnosis at randomization.
4. Subjects deemed by the treating physician as having inadequate response, loss of response or intolerance to the conventional treatment (oral 5-ASA, immune-suppressants or corticosteroids), or previously exposed to anti-TNF therapy (e.g. infliximab, adalimumab) or other biological treatment (e.g. Vedolizumab) having discontinued the treatment for:
 - Infliximab: a minimum of 8 weeks prior to baseline
 - Adalimumab: a minimum of 10 weeks prior to baseline
 - Ustekinumab: a minimum of 14 weeks prior to baseline
 - Vedolizumab: a minimum of 17 weeks prior to baseline
 - For the other biological treatments, they should discontinue for a minimum of 5 half-lives prior to baseline.
5. If subjects are currently receiving the following treatment for UC, they are eligible for the study, provided they are on stable dose for the required period of time:
 - Oral 5 ASA or Sulfasalazine, stable dose for at least 2 weeks prior to baseline and during the study treatment period.

AND/OR

- Oral corticosteroids (prednisolone \leq 30mg/day or less or equivalent) stable dose for at least 2 weeks prior to baseline. This is not applicable to the subjects who have only exposed to 5-ASA previously as per inclusion criteria 4.

6. Subject must have no evidence of active, latent, or inadequately treated infection with *Mycobacterium tuberculosis* (i.e., tuberculosis [TB]), as defined by the following:

- A negative Mantoux Purified Protein Derivative (PPD) skin test result (\leq 5 mm of induration), or negative QuantiFERON TB Gold (QFT Gold test) /or T-Spot test performed within the 3 months prior to/within screening;

AND

- Subject must have a chest radiograph, taken within the 3 months prior to/within screening, and showing no changes suggestive of active TB infection.

AND

- Subject must have no history of either untreated or inadequately treated latent or active TB infection

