5.12 Time and Event Table

See [Table1](#).**Table 1. Time and Event Table**

[figure not shown]
Period	Screening	Baseline	Treatment Phase		End of Treatment Phase	Extension Phase		End of Extension Phase	Follow-up/EW ¹¹
VISIT	1	2	3	4	5	6	7	8	9
Week	-4 to -1	0	1	4	8	9	12	16	18
Day	-28 to -1	0	7± 2 days	28± 3 days	56± 3 days	63± 2 days	84± 3 days	112± 3 days	126± 5 days
Procedures									
Written Informed Consent ¹	x								
Demography/Medical History	x								
Physical Examination	x	x	x	x	x	x	x	x	x
Chest X-ray ²	x								
Inclusion/Exclusion Criteria	x								
Randomisation Criteria		x							
Study medication dispensing		x		x	x		x		
Study medication accountability				x	x		x	x	x ¹²
Register Visit in IVRS ³	x	x		x	x		x	x	x ¹²
Endoscopy (colonoscopy) ⁴		x ⁴			x				x ¹²
Efficacy Assessments									
Patient Diary ⁵	x	x	x	x	x	x	x	x	x
Mayo Score		x			x				x ¹²
9-point Modified Mayo Score		x			x				x ¹²
Partial Mayo Score		x	x	x	x	x	x	x	x
Safety Assessments									
12-lead ECG	x	x		x	x	x		x	x
Vital Signs ⁶	x	x	x	x	x	x	x	x	x
Adverse Event Assessment ⁷		x	x	x	x	x	x	x	x
Laboratory Assessments									

Period	Screening	Baseline	Treatment Phase		End of Treatment Phase	Extension Phase		End of Extension Phase	Follow-up/EW ¹¹
VISIT	1	2	3	4	5	6	7	8	9
Week	-4 to -1	0	1	4	8	9	12	16	18
Day	-28 to -1	0	7± 2 days	28± 3 days	56± 3 days	63± 2 days	84± 3 days	112± 3 days	126± 5 days
Procedures									
Haematology and Chemistry Tests	X	X	X	X	X	X	X	X	X
Urinalysis	X	X	X	X	X	X	X	X	X
Lipid Profile (Fasting)		X		X	X	X		X	X
TSH, fT4, fT3	X	X	X	X	X	X	X	X	X
QuantiFERON /or T-Spot /or PPD test ⁸	X								
Hep B sur Ag, Hep C Ab, HIV test	X								
Stool culture/ microscopy	X								
CRP	X	X	X	X	X	X	X	X	X
Faecal Calprotectin		X		X	X			X	
Urine Pregnancy Test ⁹		X	X	X	X	X	X	X	X
β-HCG (blood) ¹⁰	X								
FSH ¹⁵	X								
Medication									
Concurrent Medication Assessment	X	X	X	X	X	X	X	X	X

1. Written informed consent must be obtained prior to performing any Visit 1 procedures or initiating any alterations in a subject's medications
2. Only to be performed if there is no chest X-ray or CT scan available within 3 months of Visit 1
3. IVRS is a randomisation machine used to record all the patient visit.
4. Colonoscopy is completed by baseline (visit 2 – Day 0). The duration of time between endoscopy and baseline is no more than -10 days.
5. Subject use an electronic diary to record disease related medical problems experienced during the study.

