6. Vital signs include resting blood pressure, heart rate, and body temperature. It is advised to measure them before any procedures or questionnaires.
7. Adverse events and Serious Adverse Events to be collected from the start of the study drug (visit 2) until the Follow-Up contact. However, any serious adverse events will be recorded from the time of consent.
8. Investigator has the option to use PPD test, QuantiFERON Gold test or T-Spot for TB screening. Subjects who have previously receive BCG vaccination will be tested by QuantiFERON Gold test/or T-Spot test, and the result will determine the subject eligibility for participation.
9. Urine pregnancy test to be done in females of childbearing potential only

10. β -Human Chorionic Gonadotrophin(β -HCG) to be done in females of childbearing potential at screening visit, and only to be done if urine pregnancy test positive at other study visits.
11. Early withdrawal visit should be done within 2 weeks after last dose/decision of withdrawal.
12. Only to be conducted in the early withdrawn subjects.

15. FSH to confirm postmenopausal status at screening visit only.

6. Study Treatments

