7.3.4 QuantiFERON test/or T-Spot test

At the discretion of the investigator, a QuantiFERON Gold®TM ([11](#)) test /or T-Spot test ([11](#)) conducted in local lab may be substituted for the PPD skin test. A description of the QuantiFERON Gold test follows: “This Enzyme-linked Immunosorbent Assay (ELISA) test detects the release of Interferon-gamma (IFN- γ) in fresh heparinized whole blood from sensitized persons when it is incubated with mixtures of synthetic peptides simulating two proteins present in *M. tuberculosis*: Early Secretory Antigenic Target-6 (ESAT-6) and Culture Filtrate Protein-10 (CFP-10). ESAT-6 and CFP-10 are secreted by all *M. tuberculosis* and pathogenic *M. bovis* strains. Because these proteins are absent from all Bacille Calmette-Guérin (BCG) vaccine strains and from commonly encountered Non Tuberculous Mycobacteria (NTM) except *M. kansasii*, *M. szulgai*, and *M. marinum*, QFT-G is expected to be more specific for *M. tuberculosis* than tests that use tuberculin Purified Protein Derivative (PPD) as the antigen”.

T-Spot is another IFN- γ release assays in diagnosing *M. tuberculosis* infection. For this test, peripheral blood mononuclear cells (PBMCs) are incubated with two mixtures of peptides, one representing ESAT-6 and the other representing CFP-10. The test uses an enzyme-linked immunospot assay (ELISpot) to detect increases in the number of cells that secrete IFN- γ .

In the situation QFT-G or T-Spot is unavailable by local testing, incubated whole blood sample could be sent to central lab for QFT-G testing. If QFT-G/or T-Spot result is indeterminate, a retest is required at earliest to determine the eligibility of the subject. If retest is indeterminate or positive, the subject should be screen failed. If retest is negative, the PI should assess the subject's clinical condition and decide if the subject could be included.

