## 3.3 CHANGES TO ANALYSIS FROM PROTOCOL

- Two new analysis sets which are all patients enrolled set and all patients randomized set have been added in this SAP. The reason for these changes is to summarize patient disposition clearly.
- In protocol, per protocol set is defined as all patients from FAS who do not have significant protocol violation. Based on the data before the interim database lock, there are some subjects who do not have primary efficacy results at week 8. In order to assess the primary efficacy results based on observed results without non-completers considered failure (NCF) imputation, these subjects without week 8 efficacy results will be excluded from PP set.

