## 9. DISPOSITION AND WITHDRAWALS

All patients who provide informed consent will be accounted for in this study.

Patient disposition and withdrawals will be presented for the enrolled population. The breakdown of patients into the analysis sets (ENR, RND, FAS, SS, and PPS) will be presented.

Follow up time (days) is time between a specified event (death, end of the study or the cut-off

Document:

\\ieedc-vnasc01\\Biosdata\\Reistone\\SHR0302\\CZA55021\\Biostatistics

Author:

██████████

Version Number:

Final v1.2

Version Date:

23Mar2021

Template No: CS\_TP\_BS016 Revision 5  
Effective Date: 01Apr2018

Reference: CS\_WI\_BS005

date for dry run or SRC analysis, whichever occurred first) and the date of randomization. Follow up time will be summarized for RND.

- Follow-up time (days) = the date of event-the date of randomization +1

Number and percentage of patients allocated to treatment will be presented by previous exposure to TNF $\alpha$ /biological treatment for RND.

Number and percentage of patients allocated to treatment in each country and site will be presented by treatment group for RND.

A listing of inclusion/exclusion criteria deviations and reason for screen failure will be provided for screen failure patients.

Additionally, any protocol deviations identified during the course of the study will be listed and the number and percentage of patients in each type of protocol deviations will be summarized for the randomized population.

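### A PPD induration of exactly 5 mm is negative under inclusion criterion 6 and positive under Protocol 7.3.3, and neither rule is given precedence

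*Protocol*

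**What the plan says.** Criterion 6 in Protocol 5.2 opens with the requirement "Subject must have no evidence of active, latent, or inadequately treated infection with" *M. tuberculosis*, and then sets out what that means in three joined conditions: a negative test, a clear chest radiograph and no history of untreated or inadequately treated TB. The test condition names a negative Mantoux PPD. It prints a less-than-or-equal sign directly before the words "5 mm of induration), or negative QuantiFERON TB Gold (QFT Gold test) /or T-Spot test performed within the 3 months". A reading of 5 mm is therefore negative, and a negative blood test is an accepted alternative.

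Protocol 7.3.3 describes the same skin test and also ties it to eligibility. Its rule is: "The test is positive if the induration's diameter (not erythema) is ≥ 5 mm 48 to 72 hours after injection". A reading of 5 mm is therefore positive.

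Three other places bear on the scope:

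- The Time and Event Table (Protocol 5.12) schedules "QuantiFERON /or T-Spot /or PPD test" at screening only. Its footnote 8 states: "Investigator has the option to use PPD test, QuantiFERON Gold test or T-Spot for TB screening".
- Footnote 8 and section 7.3.3 both send subjects with prior BCG vaccination to a blood test in place of PPD.
- Protocol 7.3.4 deals with an indeterminate blood test, which must be repeated: "If retest is indeterminate or positive, the subject should be screen failed".

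**The concern.** One reading of one test gets two opposite labels, and both labels govern entry. Section 5.2 requires every inclusion criterion to be met, and section 7.3.3 makes the skin test a condition of eligibility, so neither can be dismissed as background description.

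What is at stake is a safety threshold. TB screening precedes dosing with a JAK inhibitor. A site working from criterion 6 can accept a skin test that the section defining the test calls positive, while another site working from 7.3.3 would reject the same subject. It would also be unclear afterwards whether an accepted subject had failed an entry criterion, which is one of the situations that the stopping criteria in Protocol 5.9 address.

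**Working it through.** The plan states no figure to reproduce here. The check is a comparison of two intervals, followed by a search for text that settles any overlap.

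**Inputs.** Let x be the induration in mm. Criterion 6 (Protocol 5.2): negative if x ≤ 5. Protocol 7.3.3: positive if x ≥ 5.

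**Side by side.**

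| Reading | Criterion 6 | Section 7.3.3 | Agree? |
|---|---|---|---|
| x < 5 | negative | not positive | yes |
| x = 5 | negative | positive | no |
| x > 5 | not negative | positive | yes |

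The overlap is {x ≤ 5} ∩ {x ≥ 5} = {5}, a single value.

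**Is there a tie-breaker?** None was found.

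- Footnote 8 of the Time and Event Table covers the choice of test and prior BCG. It gives no cut-off in mm.
- Section 7.3.4 covers the blood tests and indeterminate results. It gives no PPD cut-off.
- Exclusions 13 and 32 (Protocol 5.3) leave room for the investigator's judgement. They set no threshold.
- The opening of criterion 6 rules out evidence of latent infection, but whether a 5 mm reading is such evidence is exactly what the two rules dispute.
- The SAP does not address PPD.

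**Who can be affected?** All of the following must hold:

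1. No prior BCG vaccination; otherwise a blood test replaces the PPD.
2. The investigator chose PPD rather than a blood test.
3. The reading is exactly 5 mm.
4. There is no QuantiFERON or T-Spot result. With a negative blood test, the test condition of criterion 6 is met whatever the skin test shows.

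Such a subject must still have a clear chest radiograph and an acceptable TB history.

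**Could a symbol have been misread from the PDF?** Both rules stand in the current protocol body. The Amendment 01 log reprints criterion 6 with ≤ and section 7.3.3 with ≥, before and after the change, so each operator appears three times without variation. This makes a reading error unlikely but does not prove its absence. The log is not perfectly consistent with such symbols: its Amendment 01 steroid-taper text has < 10 mg/day where current section 6.6.1 has ≤ 10 mg/day.

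**After the change.** With criterion 6 at x < 5 and section 7.3.3 at x ≥ 5, the two regions do not overlap and together cover every reading. A 5 mm reading is then positive only.

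**The case against.** The strongest reply is that both texts can be obeyed. No passage obliges a site to enrol a subject with a 5 mm reading, so a site that treats 5 mm as positive breaches nothing. Harm requires a site to apply the parenthesis in criterion 6 and overlook the section that defines a positive test. The investigator can also refuse entry under exclusion 32, or under exclusion 13 for an infection history judged liable to worsen with participation. All of this stands. It keeps the point small, but it does not tell a site which cut-off applies.

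One could also argue that a formal inclusion criterion prevails by convention. The documents do not say so, and if it did, the protocol would be admitting a test result that its own test section calls positive.

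Three stronger readings are tempting and should not be drawn:

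- A reader might infer that a subject with a 5 mm PPD and a positive first blood test is also caught, because criterion 6 joins the tests by *or*. That takes the *or* apart from its opening requirement of no evidence of latent infection. A positive blood test is such evidence, and section 7.3.4 treats the blood test as a substitute for the PPD.
- A reader might infer that the SAP would lose sight of an affected subject, since section 9 says: "A listing of inclusion/exclusion criteria deviations and reason for screen failure will be provided for screen failure patients". The same section also plans a listing of any protocol deviations identified during the study, with a summary by type for the randomized population. A place for such a subject exists. The remaining difficulty is that a site following criterion 6 may not recognize a deviation to report.
- A reader might infer that subjects with latent TB were enrolled. The documents give no BCG share, PPD share or distribution of readings, so they support no such statement.

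**Conclusion.** The inconsistency is real and lies in the current text: a PPD of exactly 5 mm is negative under criterion 6 and positive under section 7.3.3, with no stated precedence. Severity is minor. It concerns one reading value in a narrowly defined subject, and it has a cautious reading that satisfies both rules. It has no effect on the efficacy analysis, sample size or alpha. No patient count can be derived. It deserves correction because it is a decision threshold in a safety screen rather than a slip in background text.

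The conclusion assumes that the printed operators are those of the source document.

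**What to change.** Change criterion 6 to a negative PPD of < 5 mm of induration, keep section 7.3.3 at ≥ 5 mm, and notify sites. Moving section 7.3.3 to > 5 mm would also remove the overlap, but it would make a 5 mm reading negative. The first option is preferable because it errs on the side of safety. The cost is a one-symbol amendment with IRB/IEC approval under Protocol 10.2 and a short site notice. Nothing in the analysis changes.

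Enrolment may well be complete. SAP 3.3 justifies a change with the words "Based on the data before the interim database lock", and SAP 4.2 places that interim analysis after all patients have had the opportunity to complete the week 8 visit. In that case a brief check for any randomized subject admitted on a 5 mm PPD without a negative blood test is optional. Any subject found can go into the deviation listing already planned in SAP 9. The documents do not say that induration in mm is recorded in the eCRF, so the check may need source records.
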